Session 1 (Baseline, Pre-Fitting). All testing will be completed separately in each ear for all groups. Otoscopy will be performed and cerumen management completed as needed. The standard audiometric evaluation including air- and bone-conduction pure-tone audiometry; word-recognition in quiet (NU-6 words) and in noise (WIN) will be completed. Tympanometry and aural acoustic reflexes also will be measured. The COSI will be completed to obtain the listening goals of the participant and to facilitate programming needs of the replacement hearing aids (e.g., whether or not manual programs are needed/desired). In addition, an intake form (**Appendix 2**) will be completed for all groups to determine other device options and function (e.g., volume control options such as yes/no or unlinked/linked; removal filament or not; earmold style from previous order form; and tubing length; etc.). If care or use questions arise based on responses on the intake form, then they will be answered during this session. The replacement hearing aids and earmolds will be ordered using the earmold scans on file with the manufacturer provided that the current earmolds from the old hearing aid are a good fit. If not, then ear impressions will be made for replacement earmolds.

For the experimental groups, the tubing length of the current earmolds will be measured carefully so that the replacement earmold tubing can be cut to the same length at the RECD-fitting (Session 2-below). For the Exp-AVGc group, the current earmold vent size will be measured if the actual size is not available on the previous order form. That way, the average RECD values can be corrected for the vent size of the earmold at the RECD-fitting (Session 2).

For the Exp-M group only, RECD values will be obtained separately for each ear with the patient's current earmolds after they have been cleaned and tubing changed as needed. Using the current earmold as opposed to the foam insert will allow venting and tubing characteristics to be incorporated in the RECD-fitting. The RECD measurement protocol will follow the standard clinical protocol and will use the Verifit 2 system. The test box reference microphone will be calibrated. The RECD transducer will be placed on the BTE coupler and the coupler response will be obtained. The probe tube will be inserted 25-27 mm from the antitragal notch in order to ensure placement

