within approximately 2-5 mm from the eardrum. The participant's current earmold (lubricated to ensure a good seal) will be placed in the ear canal and care will be taken not move the probe tube during earmold insertion. The RECD transducer will be coupled to the earmold tubing and the realear response will be obtained. The difference between the coupler and real-ear responses is the measured RECD.

Session 2: The Intervention 'Visit'.

Soc Group Fitting. This group will receive the SoC, 30-minute face-to-face fitting appointment 4-6 weeks after Session 1, the average wait time for a fitting appointment. The right and left hearing aids will be programmed separately to the National Acoustics Laboratory Non-Linear 2 (NAL-NL2) prescription. The REAR of the hearing aids will be verified to the 50-, 65-, and 75-dB SPL prescriptive targets generated by the Verfit 2 system using the speechmap stimulus. The criterion for an appropriate fitting would be ± 3 dB between the output and the prescriptive target from 250 Hz to the frequency in which the unaided threshold crossed the 65-dB SPL target. The Real Ear Saturation Response (RESR) will be measured using an 85-dB swept pure-tone to ensure that the maximum output of the hearing aids does not exceed the predicted uncomfortable loudness levels of the participant. The programming options will be optimized based on the information obtained on the intake form (**Appendix 2**). The participant will be provided with the manufacturer brochure, programming report from the manufacturer software, and the VA Hearing Aid Booklet. Consistent with current SoC, no orientation will be provided.

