Experimental Group Fittings. The participants in the experimental groups will not be present during the fitting. The hearing aids will be fitted in a manner similar to the SoC fitting except the average-corrected (for vent size) RECD (Exp-AVGc Group) or measured RECD from Session 1 (Exp-M group) will be inputted into the Verfit 2 to generate the prescriptive targets and the derived REARs will be obtained following the standard clinical procedure. In short, the tubing of the *replacement* earmold will be cut to length and coupled to each hearing aid. The earmold will be attached to the HA-1 coupler with putty ensuring that the eartip is flush against the opening of coupler and the vent sealed, as is standard with this procedure. The hearing aids will be programmed and the derived REARs will be obtained and verified against the prescription. After programming and verification, the hearing aids will be mailed to the patient along with the manufacturer brochure, programming report from the manufacturer software, and the VA Hearing Aid Booklet within one business day of their receipt from the manufacturer. It is estimated that these experimental fittings will take 15 minutes, or half the time of the SoC fittings. A signature will be required to accept the delivery and the delivery will be tracked.

Two-Day Follow-Up Phone Call. All participants will receive a 2-day follow-up phone call after the hearing-aid fitting. The experimental groups will be phoned after delivery of the hearing aid is confirmed with the delivery receipt. A telephone script (**Appendix 2**) will be used to ask questions about the physical comfort of the device, sound quality, and any other hearing-aid problems or questions.

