Session 3 (One-Month Post-Fitting). One month after the hearing-aid fitting, all groups will return to complete subjective outcome measures. The measures will be presented in random order. The COSI outcomes will be measured to determine if the hearing aids are meeting the patient-nominated goals. The SADL will be completed and the *Service and Cost* subscale will be of great interest due to the service-related items that may differentiate between groups. The DOSO will be used as it assesses hearing-aid outcomes in six domains. An exit survey (**Appendix 2**) also will be administered to gain insight into the perceptions related to service delivery, access, and convenience. In addition, *in situ* REARs will be obtained from all groups using the current programming from the replacement aids. These *in situ* REARs will allow within and between group comparisons regarding the hearing-aid function and determine the accuracy of the experimental fittings relative to the SoC fittings. The repeat *in situ* REAR measurements in the SoC group (i.e., Sessions 2 and 3) will serve to assess the inherent variability with *in situ* REAR measurements and

will facilitate interpretation of REAR data when comparing the accuracy of the *in situ* and derived REARs in the experimental groups.

Attrition. In our experience ([name] and [name]) with a multi-session (4 sessions over 6 months), hearing-aid clinical trial, we had a low local attrition rate of 8.7%. The primary reasons for withdrawal were due to personal reasons which included illness, moving out of state, and transportation issues during inclement weather (i.e., snow). Thus, we considered a conservative estimate of 15% attrition for the proposed multi-session study.

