Sample Size. Based on an expectation that REAR measurements should be within 2 dB on average across frequency, and an SD of 2, then 18 participants are needed for each group (total N = 54) assuming a power of at least β = .80 and *p* = .05. Considering 15% attrition, then 9 additional subjects will be needed (N = 63) resulting in 21 participants per group. Participants will be recruited from the Mountain Home VA audiology clinics. Last year, our clinic served 7,481 Veterans during 16,278 patient visits and dispensed 7,134 hearing aids. Also, based on the national average, it is estimated that ~50% of VA hearing aids dispensed are replacement hearing aids for experienced users. Thus, we anticipate no difficulty in recruiting the target sample at Mountain Home.

Data Analysis.

Specific Aim 1 and 2. A mixed-model analysis of variance (ANOVA) will be conducted. This analysis will examine differences (in dB SPL) for REAR (actual vs derived using average vs measured RECD) across frequency and ears within and between the groups. This analysis will determine (1) if the *in situ* REARs differ from the derived REARs in the experimental groups and if the derived REARs in the experimental groups differ from the *in situ* REARs in the SoC group (2) if coupler-derived REARs using average-corrected or measured RECDs differ; and (3) if the average-corrected RECD.

Specific Aim 3. A multivariate ANOVA will be conducted to examine group differences among the outcome measure subscales. A logistic regression also will be conducted to examine if the proportion of responses differ among the groups on the specific telephone and exit survey items of interest.

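### The between-group REAR contrast estimates the total effect of each fitting approach; without a saved reference target it cannot be read as fitting accuracy

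*Combined protocol and SAP*

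**What the plan says.** All arms use one prescription, NAL-NL2, and one analyser. What differs is how the target is produced.

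- **SoC (SoC Group Fitting).** REARs are verified in the ear against "prescriptive targets generated by the Verfit 2 system using the speechmap stimulus". No RECD entry is mentioned. The tolerance is stated here: "The criterion for an appropriate fitting would be ± 3 dB between the output and the prescriptive target".
- **Experimental arms (Experimental Group Fittings).** "The hearing aids will be fitted in a manner similar to the SoC fitting except the" average-corrected or measured RECD "will be inputted into the Verfit 2 to generate the prescriptive targets and the derived REARs will be obtained following the standard clinical procedure". Then: "The hearing aids will be programmed and the derived REARs will be obtained and verified against the prescription". The 3 dB tolerance carries over only through the likeness to the SoC fitting.
- **Source of the RECD (Session 1).** "For the Exp-M group only, RECD values will be obtained separately for each ear". Exp-AVGc uses average values corrected for vent size.
- **Analysis (Data Analysis, Specific Aim 1 and 2).** "This analysis will examine differences (in dB SPL) for REAR (actual vs derived using average vs measured RECD) across frequency and ears", within and between groups. No deviation from target, common reference target or target covariate is defined.
- **Interpretation (Session 3).** The in situ REARs from all groups are to "determine the accuracy of the experimental fittings relative to the SoC fittings".

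**The concern.** Accuracy needs a reference, and the planned between-group variable has none: it is output in dB SPL. Two participants with the same audiogram may be fitted to different targets because different RECDs were entered. If the arms then differ in mean REAR, the output may have missed its target, or the target may have been placed elsewhere. The planned analysis would show the same number in both cases.

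This affects the comparison of experimental derived REARs with SoC in situ REARs (second half of Aim 1), the comparison of average-corrected with measured RECD fittings (Aim 2), and the Session 3 comparison with SoC. It matters for the trial's message. A shifted target is a property of the prescription step, while a missed target is a failure of fitting without the patient present. A reader deciding whether mailed fittings are acceptable would want to know which occurred.

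Raw dB SPL also varies between people because their audiograms call for different output. That variance has nothing to do with accuracy and reduces the precision of the group comparison.

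**Working it through.** **1. The plan's own figure.** Inputs from Sample Size: difference 2 dB, SD 2 dB, alpha 0.05 (two-sided assumed), power 0.80. The normal formula gives n = 2 × (1.960 + 0.842)² × (2/2)² = 15.7, so 16 per group. The t-based version gives 16.7, so 17. At the stated 18 per group, t-test power is 0.83. The figure reproduces within two participants, and the point below is not an arithmetic error.

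**2. Decomposition.** For one ear let C be a common target from the Session 1 audiogram, generated as in SoC; T the target actually used; and R the Session 3 in situ REAR. Then

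R − C = (T − C) + (R − T), that is, total effect = target shift + delivery error.

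- *Raw R between groups.* C depends only on baseline data, so randomisation gives it the same expected mean in every arm. The expected group difference in R equals that in R − C: shift and error combined.
- *R − C.* Same expected difference. Subtracting C removes audiogram-driven variance and supplies a reference, but the two components remain summed.
- *R − T.* The shift cancels and delivery error is left. Used alone, it hides the shift.
- *T − C.* The shift alone. In SoC it should be zero, if the target used comes from the same audiogram with no RECD entered.

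Example with invented values for an experimental arm against an SoC arm with no shift and no error: shift 1 dB with error 0 gives a raw difference of 1 dB; shift 0 with error 1 dB also gives 1 dB; shift 1 dB with error −1 dB gives 0. The raw contrast cannot separate the first two and shows nothing in the third.

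**3. Would a wrong RECD stay hidden?** Let D be the derived REAR. Then R − T = (R − D) + (D − T). The entered RECD feeds both D and T, so the Session 2 check on D − T need not reveal an error in it. But R is measured in the ear, so R − D would. That is the within-ear contrast in the first half of Aim 1, and it does not depend on the target.

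**4. Size under assumptions.** The documents give no target shift. With SD 2 dB, 18 per group, a two-sided 0.05 t-test and identical delivery error in both arms:

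| Assumed mean shift | Chance of a significant raw difference |
|---|---|
| 0 dB | 5% |
| 0.5 dB | 11% |
| 1 dB | 31% |
| 1.5 dB | 59% |
| 2 dB | 83% |

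In the other direction, a true 2 dB delivery difference offset by an opposing 1 dB shift leaves a net 1 dB, detected with 31% power instead of 83%.

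**5. Precision.** Suppose the plan's SD of 2 dB describes deviation from the common target, and targets vary between people with an assumed SD s. The raw SD is then √(4 + s²). Power for a 2 dB difference at 18 per group:

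| Assumed s | Raw SD | Power, raw REAR | Power, REAR minus common target |
|---|---|---|---|
| 2 dB | 2.83 dB | 54% | 83% |
| 4 dB | 4.47 dB | 26% | 83% |
| 6 dB | 6.32 dB | 15% | 83% |

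If the SD of 2 dB already describes raw REAR between people, this gain is smaller. The plan does not say which it describes.

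**The case against.** The strongest reply is that target dependence on the RECD is part of the intervention. The opening statement of purpose describes approaches that use the RECD for both fitting and verification, and Aim 2 asks whether the resulting fittings differ. The raw contrast answers that as a total effect. This stands: the comparison is neither biased nor invalid as an estimate of the whole approach. What does not follow is calling that total effect accuracy.

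Second, the trial already has a sound accuracy test within the ear, read against the repeat SoC measurements. This also stands. A reader might infer that a wrong RECD would go unnoticed because its own target moves with it. That holds only for the Session 2 coupler check; the Session 3 measurement would expose the error.

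Third, the size is unknown. This stands too. The documents do not say which RECD, if any, underlies the SoC target. Silence in a short description does not show a materially different target, and the gap between SoC and Exp-AVGc may be only the vent correction. Measured RECDs scattered around the average could largely cancel in a group mean. The percentages above follow from assumed shifts and are not evidence that any shift exists.

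Fourth, an SoC-style yardstick favours SoC, which is fitted to it by design. That is a reason to report both components. The choice is still consistent with the Session 3 section, which defines accuracy relative to SoC.

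**Conclusion.** The point holds in a limited form. The between-group contrast of raw REAR is a valid randomised estimate of the total effect of each fitting approach, but it does not measure accuracy as the Session 3 section uses the word. It lacks a reference target, carries audiogram-driven variance, and merges target shift with delivery error. The within-ear comparison of derived and in situ REAR is not touched.

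The size cannot be established from the documents. Assumed mean shifts of 0.5 to 2 dB would make an apparent accuracy difference significant 11% to 83% of the time; with no shift the rate is the nominal 5%. These figures rest on the plan's SD of 2 dB, 18 per group and a two-sided t-test.

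Two further inferences are not supported. Subtracting a common target does not by itself undo the mixing, because the expected group difference is unchanged. Nor is deviation from the ear's own target uninformative: it removes the shift and isolates delivery error. The change is worth making because it is cheap and turns an unknown shift into a reported number.

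**What to change.** Leave the fittings unchanged. For every ear in all three arms, save:

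- (a) the target actually used; and
- (b) one common NAL-NL2 target set at 50, 65 and 75 dB SPL, generated from the Session 1 audiogram in the SoC manner with no arm-specific RECD entered.

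In Data Analysis, specify Session 3 in situ REAR minus (b) as the between-group outcome and label it the total effect. Report its two components by arm: (a) minus (b), the target shift; and in situ REAR minus (a), the delivery error. State that subtracting (b) supplies the reference and may improve precision but does not alone separate the components. Keep derived versus in situ REAR as the within-ear accuracy test. State also which RECD, if any, underlies the SoC targets.

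The cost is one extra saved target screen per ear, some added analysis and a few sentences of plan text. There is no added patient contact and no change to care.

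### The Session 3 in situ REAR is taken at the aid's current settings, so any change since Session 2 would be read as error of the derived fitting or, in SoC, as retest variability

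*Combined protocol and SAP*

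**What the plan says.** In the experimental groups the aid is programmed at Session 2 without the participant, and "the derived REARs will be obtained and verified against the prescription" before mailing (Experimental Group Fittings). The SoC group has its in situ REAR at the Session 2 appointment. Then "One month after the hearing-aid fitting, all groups will return", and an in situ REAR is taken in every group "using the current programming from the replacement aids" (Session 3).

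The Session 3 measurement has two uses. It is to "determine the accuracy of the experimental fittings relative to the SoC fittings", and Data Analysis makes in situ versus derived REAR in the experimental groups the first Aim 1 question. In SoC, the repeat in situ "REAR measurements in the SoC group (i.e., Sessions 2 and 3) will serve to assess the inherent variability with" this kind of measurement, and the result is to guide the reading of the experimental data.

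Two other parts of the text bear on whether settings stay the same. The Two-Day Follow-Up Phone Call asks every participant "questions about the physical comfort of the device, sound quality, and any other hearing-aid problems or questions". The Session 1 intake form records device options, including "volume control options such as yes/no or unlinked/linked", and the COSI helps decide whether manual programs are wanted.

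**The concern.** Both uses of the Session 3 REAR assume that the aid has the same settings as at Session 2. In the experimental groups, in situ minus derived measures the accuracy of the RECD method only if the hearing aid itself is unchanged. In SoC, the Session 2 to Session 3 difference measures repeatability only on the same condition.

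The stated rule does not secure that condition. The experimental groups have a single in situ REAR, so a settings change cannot be separated from RECD error afterwards. In SoC, a change cannot be separated from probe-placement and other retest error. Mistakes in both directions are possible: an accurate derived fitting may look inaccurate, or an inflated SoC yardstick may excuse an inaccurate one.

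**Working it through.** **1. Which contrasts use Session 3 data.** Setting the questions in Data Analysis (Specific Aim 1 and 2) and the stated use of the SoC repeat against the session at which each REAR is obtained:

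| Comparison | Sessions | Affected by a settings change? |
|---|---|---|
| In situ vs derived, within experimental groups (Aim 1) | 3 vs 2 | Yes |
| SoC repeat in situ (variability yardstick) | 3 vs 2 | Yes |
| Derived (experimental) vs in situ (SoC) (Aim 1) | 2 vs 2 or 3 (not stated) | Not if SoC Session 2 is used |
| Derived, average-corrected vs measured RECD (Aim 2) | 2 vs 2 | No |

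**2. The plan's own figure.** Sample Size gives a 2 dB difference, SD 2, alpha .05, power .80 and 18 per group. Two groups, two-sided, normal approximation: n = 2 × (1.960 + 0.842)² × (2/2)² = 15.7, so 16 per group; the t-test version gives 17. The stated 18 meets the power target. This point does not change the sample size.

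**3. Size of the effect on the within-group contrast (illustration).** Inputs from the document: n = 18, and 2 dB as the planning difference. Assumptions:
- A share p of participants has settings changed by d dB, all in one direction. The documents give neither p nor d.
- The SD of the paired difference without any change is 2 dB. The document gives an SD of 2 but does not say that it is the SD of this difference.
- The derived fitting is exact, so the true mean difference is 0.

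Formulas: false mean error = p × d; SD = √(2² + p(1 − p)d²); noncentrality of the paired t-test = (p × d / SD) × √18, with 17 degrees of freedom, two-sided .05.

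| p | d (dB) | False mean error (dB) | SD (dB) | Noncentrality | Declared different |
|---|---|---|---|---|---|
| 5% | 3 | 0.15 | 2.10 | 0.30 | 0.059 |
| 10% | 3 | 0.30 | 2.19 | 0.58 | 0.085 |
| 20% | 3 | 0.60 | 2.33 | 1.09 | 0.178 |
| 30% | 5 | 1.50 | 3.04 | 2.09 | 0.506 |

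The last row in full: 0.3 × 5 = 1.5; √(4 + 0.21 × 25) = √9.25 = 3.04; 1.5/3.04 × 4.243 = 2.09.

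The table treats the differences as normal. Simulating the actual mixture of changed and unchanged participants gives about 0.08 for 10% at 3 dB and 0.49 for 30% at 5 dB, so the approximation is adequate.

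**4. Changes in both directions.** With increases and decreases equally likely, the mean error is 0 and SD = √(2² + p × d²). This is √4.9 = 2.21 dB for 10% at 3 dB and √11.5 = 3.39 dB for 30% at 5 dB. The false rejection rate stays near .05, but the spread grows. In SoC, that extra spread would be read as measurement variability.

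**The case against.** The strongest objection is that the documents do not show that any aid is changed. No adjustment visit is scheduled, the two-day call is described only as asking questions, and current programming may simply mean the programming already stored in the new aids. Volume control and manual programs are options, so not every aid has them. The telephone script and intake form are in Appendix 2, which is not in the supplied text and could contain a rule on handling problems. All of this stands, and it makes the point conditional: if no aid is changed, there is no error. It does not remove the point, because nothing in the available text secures unchanged settings or would reveal a change.

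A second objection is that SoC is measured under the same rule and so provides a concurrent reference. This holds only in part. Changes may be more or less frequent after a mailed fitting than after a face-to-face one, and in SoC they would be labelled as measurement variability.

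A third is that the REARs also describe hearing-aid function, for which as-worn settings are reasonable. That is fair, and it is a reason to report an as-worn measurement separately. It does not make that measurement a test of the derived fitting.

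A reader might go further and infer that all Aim 1 and 2 contrasts are biased, or that the power of the two-group comparison behind the sample size is lost. The documents do not support either. The Aim 2 comparison in Data Analysis uses only values obtained before mailing, and the derived versus SoC comparison can be made wholly within Session 2.

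**Conclusion.** The point holds in conditional form. The rule for the Session 3 REAR leaves the within-group in situ versus derived contrast of Aim 1, and the SoC repeatability yardstick, open to any change of gain, program or volume during the intervening month, and the plan as supplied cannot detect such a change.

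The size is unknown. In the one-directional illustration the false mean error is 0.3 to 1.5 dB against a planning difference of 2 dB, with an exact fitting declared different about 9% to 51% of the time. At 5% changed by 3 dB the rate is about 6%, close to nominal. These figures depend on the assumed rates, on one direction of change, and on reading the SD of 2 dB as that of the paired difference. They show what could happen and are not a forecast. The change is worth making because it is cheap, and because without saved settings the ambiguity cannot be resolved once the data are collected.

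**What to change.** In the Session 3 procedure:

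- Save the settings file of each aid at Session 2 (after verification) and again on arrival at Session 3.
- Take the accuracy REAR with the Session 2 verified settings recalled and volume and program at default, then put the participant's own settings back.
- If an as-worn REAR is wanted, report it separately as a description of hearing-aid function and keep it out of the accuracy contrast and the SoC repeatability estimate.

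In Data Analysis, state that the derived versus SoC comparison uses the SoC Session 2 in situ REAR.

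The cost is a few sentences and, by this review's estimate, a few more minutes at a visit that already includes a REAR. The number of participants does not change.

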- no more than a moderate sensorineural hearing loss (defined as < 60 dB HL pure-tone average at 500, 1000, and 2000 Hz AU)
- ability to read and write in English as determined by reading a few sentences from the consent document aloud so that self-report measures can be completed

Exclusion Criteria: Participants will be excluded if any of the following criteria are true:

- outer or middle ear pathology as determined by otoscopy, immittance, and/or audiometric testing (e.g., conductive or mixed losses)
- lack of phone or non-use of the phone as the participants will be required to conduct a telephone interview after they obtain their replacement hearing aids
- unwilling or unable to be mailed hearing aids
- co-morbid condition that would preclude their participation as determined by a chart review (e.g., dementia, visual impairment/legal blindeness, substance abuse, etc.)

Materials/Tests:

In addition to RECD and REAR measures, this study will include measures of speech-in-noise abilities and hearing-aid outcomes. These measures are described below:

Client-Oriented Scale of Improvement (COSI; Dillon, James, & Ginis, 1997). The listener nominates up to five listening goals on the COSI. After hearing-aid use, the listener assesses two outcomes for each goal. One outcome is the "degree of change" relative to the patient's unaided experience. Responses are recorded on a categorical scale from 'worse' to 'much better.' The second outcome is the final satisfactory "aided" ability for each goal as measured on a categorical scale from hardy ever (10%) to almost always (95%). The percentage of 'better' and 'much better' responses and the average of the final ability will be calculated across goals. (Session 1—goals established and Session 3—outcomes established—See Procedure Section below) (5 minutes). Device Oriented Subjective Outcome (DOSO) Scale (Cox, Alexander, & Xu, 2009). The questionnaire is comprised of 28 items making up the following six subscales related to listening performance with hearing aids: (1) speech cues, (2) listening effort, (3) pleasantness,(4) quietness, (5) convenience, and (6) use. Responses from 'not at all' (1 point) to tremendously (7 points) are recorded for each item. Higher scores represent better device-oriented subjective outcome. This is a post-only measure (Session 3) (10 minutes).

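### The one-month questionnaires are collected only at an in-person return visit, so a participant who has the aids but cannot travel is lost from every Aim 3 measure except the 2-day telephone items

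*Combined protocol and SAP*

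**What the plan says.** Under Session 3 (One-Month Post-Fitting), "all groups will return to complete subjective outcome measures". The COSI outcomes, SADL and DOSO are given there in random order, and an exit survey "also will be administered to gain insight into the perceptions related to service delivery, access, and convenience". The in situ REAR is measured at the same visit. No other way of completing the questionnaires is described. The DOSO is taken only after fitting and the SADL is listed only at Session 3, so neither has a baseline score.

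The Attrition section reports 8.7% loss in the investigators' earlier trial (four sessions over six months) and plans for 15% here. On the causes in that trial it says: "The primary reasons for withdrawal were due to personal reasons which included illness, moving out of state, and transportation issues during inclement weather". The Sample Size section responds by enrolling 63 instead of 54.

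There is one earlier subjective contact: "All participants will receive a 2-day follow-up phone call after the hearing-aid fitting". It covers physical comfort, sound quality and other problems or questions. Specific Aim 3 uses these data, since a logistic regression compares response proportions "on the specific telephone and exit survey items of interest". For the scales, "A multivariate ANOVA will be conducted to examine group differences among the outcome measure subscales". No missing-data method is given.

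The Exclusion Criteria rule out "lack of phone or non-use of the phone as the participants will be required to conduct a telephone interview", and also anyone who cannot or will not be mailed hearing aids. The inclusion criteria require reading and writing English so that self-report measures can be completed.

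**The concern.** Of the Session 3 measures, only the in situ REAR needs the participant in the clinic. The questionnaires are self-report, and everyone enrolled can by design be reached by telephone and by mail. Tying the questionnaires to the visit discards answers that could still be had from people who are wearing the aids but are ill, have moved or cannot travel.

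The stakes are highest where the outcome is itself about access. The plan singles out the SADL Service and Cost subscale as likely to separate the groups, and the exit survey asks about delivery and convenience. Difficulty in reaching the clinic could plausibly influence both whether someone returns and how that person rates mailed or face-to-face delivery. A multivariate ANOVA in its standard form drops incomplete cases, and with no baseline SADL or DOSO score there is little from which to impute. Over-enrolment protects precision but not against selection of this kind.

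**Working it through.** **The plan's own figures.** Sample Size gives a 2 dB difference, SD 2, power 0.80 and p = .05. A two-sided test is assumed because sidedness is not stated. The normal approximation gives 16 per group and the two-sample t-test 16.7, so 17. The stated 18 has t-test power 0.83 and is reproduced closely enough. For attrition, 54 × 1.15 = 62.1, which rounds up to 63 in three equal groups of 21; dividing instead gives 54 / 0.85 = 63.5, or 64. These figures are for REAR. The plan gives no effect size or SD for Aim 3.

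**Numbers left at Session 3.**
- 15% loss: 63 × 0.15 = 9.45 missing (3.15 per group); 53.55 remain (17.9 per group).
- 8.7% loss: 63 × 0.087 = 5.5 missing; 57.5 remain (19.2 per group).

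The inflation therefore roughly keeps the planned 18 per group.

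**Possible shift in a group contrast.** Let p be the proportion missing and s the amount by which non-returners differ from returners. The completer mean in an arm is then off by p × s. If s has opposite signs in the mailed and SoC arms and loss is equal, the contrast is off by 2 × p × s. Assumptions, none of them in the documents: SD of 1 on a 1 to 7 scale, s of 0.5 to 1 point, and all loss after fitting. With 18 per group, SE = sqrt(2/18) = 0.333.

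| Loss | s | Shift = 2 × p × s | Shift / 0.333 |
|---|---|---|---|
| 8.7% | 0.5 | 0.087 | 0.26 |
| 8.7% | 1.0 | 0.174 | 0.52 |
| 15% | 0.5 | 0.15 | 0.45 |
| 15% | 1.0 | 0.30 | 0.90 |

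Two other patterns give less:
- Equal loss, with s the same in size and sign in every arm: p × s − p × s = 0.
- Loss of 20% versus 10% with a common s of 0.5 SD: (0.20 − 0.10) × 0.5 = 0.05 SD.

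For scale, the smallest difference detectable with 80% power at 18 per group is about 0.96 SD (two-sided t-test).

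If half of the loss came before fitting (also an assumption), the part that remote collection could address would roughly halve. With 1-point shifts it would be about 0.09 points at 8.7% loss and 0.15 at 15%.

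**Ceiling on what can be recovered.** If all 15% were lost after receiving the aids and all then answered, about 9 of 63 would be recovered and the SE would fall from sqrt(2/18) = 0.333 to sqrt(2/21) = 0.309. Any loss before fitting, or any non-response by mail and telephone, makes the gain smaller.

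**The case against.** A reader might infer that non-returners contribute nothing to Aim 3. The documents do not support that. Anyone reached by the 2-day call supplies telephone items that are analysed under Specific Aim 3. As described, those items cover comfort, sound quality and problems two days after fitting, so they do not stand in for one-month benefit and satisfaction or the exit survey. The loss is of the Session 3 measures, not of all Aim 3 data. The script itself is in Appendix 2, which is not in the text reviewed.

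A reader might also infer that SoC will lose more questionnaire data because it has an extra trip at Session 2. But Session 2 is where SoC participants receive their aids. Someone lost there has no replacement aids to rate, and remote questionnaires would not help. A mailed participant with the same difficulty would have the aids and could be recovered. Unequal loss before receipt is thus possible, and the fix below does not repair it.

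Nor is it established that mailing's advantage would be understated. Someone who cannot travel and whose mailed aid needs in-person attention could rate mailing worse.

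The remaining objections concern size and mode. The withdrawal reasons come from a longer trial, 15% is the plan's own conservative figure, and some people who withdraw will not answer by any route. These points stand and are why the size is given as a range with ceilings. A single visit is a defensible choice because the REAR requires it, and telephone administration to hearing-aid users adds a mode difference. Mailing the same written forms meets most of that last point.

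**Conclusion.** The point holds in a limited form. Collecting the COSI outcomes, SADL, DOSO and exit survey only in person gives up answers from participants who have the aids but cannot return, and the reason for their absence may be related to what these measures ask.

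Under the stated assumptions the effect on a mailed-versus-SoC contrast runs from none to 0.30 points (0.9 SE). The top of that range needs 15% loss, all of it after fitting, and full 1-point shifts in opposite directions. At the earlier trial's 8.7% the opposite-shift range is 0.09 to 0.17 points (0.26 to about 0.5 SE). These amounts are modest against a detectable difference of about 0.96 SD, and their sign is unknown. The case for change rests mainly on how little it costs. It does not show that the Aim 3 comparison is invalid as planned.

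**What to change.** Add to Session 3: a participant who has received the replacement aids but does not return is offered the COSI outcomes, SADL, DOSO and exit survey by mail on the same forms, or by telephone if mail fails, within the same one-month window. Only the in situ REAR is then missing.

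Add to Data Analysis, Specific Aim 3: these responses are included; mode of completion and reason for non-return are recorded and reported by group; and the analysis is repeated with in-clinic responses only. That repeat shows whether the conclusion depends on the remote responses, although with so few it cannot separate a mode effect from a real difference between the people. Report separately, by group, those lost before they received the aids, since this change does not recover them.

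The cost is one mailing, or about 20 to 25 minutes of existing staff time, for each of at most about nine people. The plan allows 5 + 10 + 5 = 20 minutes for the COSI, DOSO and SADL; about 5 minutes for the exit survey is assumed. The downside is a few responses in a different mode. Sample size, randomization and REAR procedures do not change.
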